#### 6.2.2.3. **Sensitivity analysis considering subjects aging when enrolled into ZOSTER-049 from ZOSTER-006/022**

*Since all subjects enrolled in ZOSTER-049 study had aged for ~5 years compared to when they were enrolled in ZOSTER-006/022 studies, a sensitivity analysis on VE (analysis A, B and C on mTVC - LTFU and Control group only.) is planned to consider the aging factor on ZOSTER-049 subjects when utilizing the historical control to estimate the incident rate on the hypothetical control in ZOSTER-049 study. Please refer to Section 7.3.6 for more details*

#### 6.2.2.4. **Additional VE sub-group analysis**

*As per CBER’s recommendation, vaccine efficacy for first or only episode of confirmed HZ episode of the ZOSTER-049 study using Poisson method on modified Total Vaccinated Cohort will also be presented by gender, race, region and ethnicity.*

*Vaccine efficacy for first or only episode of confirmed HZ episode from one month post dose 2 in the ZOSTER-006/022 studies using Poisson method on modified Total Vaccinated Cohort will also be presented by gender, race, region and ethnicity.*

### **6.3. Analysis of immunogenicity**

The primary immunogenicity analysis will be based on the ATP cohort. If, in any vaccine group the percentage of vaccinated subjects with serological results excluded from the ATP cohort for analysis of immunogenicity is 5% or more, a second analysis based on the TVC will be performed to complement the ATP analysis.

All analyses will be presented overall and by age strata. The main age strata for reporting purposes are 50-59, 60-69 and  $\geq 70$  YOA. Additional analysis will be presented in  $\geq 60$  YOA.

#### **6.3.1. Assessment for 1-Additional Dose, Revaccination and Control groups**

##### **6.3.1.1. Humoral immune response**

###### **Descriptive analysis – within group:**

The following parameters will be tabulated by vaccine group at each time point when a blood sample result is available:

- Seropositivity rate with exact 95% CI;
- GMC with 95% CI;
- The MGI Post Month 1 and Post Month 3 current study over pre-vaccination in the primary studies with 95% CI;
- The MGI Post Month 3 primary vaccination over the Post Month 1 and Post Month 3 current study with 95% CI;
- The MGI Post Month 1 and Post Month 3 current study over Visit Month 0, in the current study with 95% CI;
- The MGI Post Month 3 over Post Month 1 current study for the Revaccination and Control groups with 95% CI;
- VRR [post additional dose groups over pre-vaccination in the primary studies] with exact 95% CI;
- The distribution of Ab titres will be tabulated and also presented using reverse cumulative curves.

**Exploratory assessment – between group:**

- CCI

**6.3.1.2. Persistence analysis – Randomized groups**

Persistence data will be analysed from the Visit Year 1 to the Visit Year 6 timepoint after vaccination.

**For each year X (X varying from year 1 to year 6):** The analysis of Ab persistence will be based on the ATP cohort for persistence at year X –adapted for each timepoint. If the percentage of subjects, excluded from the ATP cohort for the Year X follow-up serological results, is higher than 5% for any group, a second analysis based on the TVC – **Randomized groups** at Year X will be performed to complement the ATP analysis.

The following parameters will be tabulated by group at each timepoint when a blood sample result is available (including Month 0, Month 1 and Month 3):

- Seropositivity rate with exact 95% CI;
- GMC with 95% CI;
- The MGI Post Month 3 primary vaccination over the Post year x for the 1-Additional Dose or Revaccination group with 95% CI;
- The MGI Post year x for the 1-Additional Dose or Revaccination group over Visit Month 0, in the current study with 95% CI;
- The MGI Post year x over pre-vaccination in the primary ZOSTER-006/022 studies with 95% CI;
- VRR [post year x (1-Additional Dose or Revaccination group) over pre-vaccination in the primary ZOSTER-006/022 studies] with exact 95% CI;
- The distribution of Ab titres will be tabulated, and also presented using reverse cumulative curves.

**6.3.1.3. Cell-mediated immune response**

Descriptive statistics (N, mean, SD, min, Q1, median, Q3, max) of the following parameters will be tabulated by group at all timepoints:

- Descriptive statistics of the frequency of CD4+ T-cells secreting at least two activation markers (from among IFN- $\gamma$ , IL-2, TNF- $\alpha$ , CD40L) for gE-specific stimulation.
- CCI

CCI

### 6.3.2. Analysis on subjects with confirmed HZ cases

The following analysis will be also performed at each time point when a blood sample result is available on subjects who had a confirmed HZ case:

For HI

- Seropositivity rate with exact 95% CI;
- GMC with 95% CI.
- For CMI
  - *Descriptive statistics (N, mean, SD, min, Q1, median, Q3, max) of the frequency of CD4+ T-cells secreting at least two activation markers (from among IFN- $\gamma$ , IL-2, TNF- $\alpha$ , CD40L) for gE-specific stimulation will be presented*

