**CONFIDENTIAL**

201190 (ZOSTER-049 EXT:006-022)  
Protocol Amendment 5 Final

**LTFU Group (CMI subset):** Subjects (N ≤ 234) who were in the CMI subset during study ZOSTER-006 and continue participation in this study. Blood samples (approximately 20 mL) will be collected and tested from Visit Month 0 to Visit Year 6 on a yearly basis to assess CMI responses.

**HZ subset:** Subjects (N to be determined) who developed confirmed HZ during ZOSTER-006 or ZOSTER-022, or who develop HZ during the interval between the end of the ZOSTER-006/022 and the beginning of ZOSTER-049, or who develop suspected HZ during ZOSTER-049 will be part of the HZ subset. Blood sampling for subjects in the HZ subset is described below.

Subjects who develop HZ at any time after enrolment in ZOSTER-006 or ZOSTER-022 and who are already part of the HI subset in ZOSTER-006 or ZOSTER-022 will provide blood samples to assess HI responses (approximately 5 mL) from Visit Month 0 to Visit Year 6 irrespective of when the HZ episode occurs. If these subjects are part of the ZOSTER-006 CMI subset, then they will also continue to provide blood to assess CMI responses (approximately 20 mL).

Subjects who develop HZ at any time after enrolment in ZOSTER-006 or ZOSTER-022 and who were NOT part of the HI or CMI subsets in these studies, will provide blood samples to assess HI responses (approximately 5 mL) beginning at the annual visit in the ZOSTER-049 study subsequent to the occurrence of the HZ episode. The blood sample taken upon enrolment at Visit Month 0 will be tested and included in the analyses for these subjects.

**1-Additional Dose Group:** Subjects (N = 60) to be administered HZ/su vaccine on a 1-dose schedule at Visit Month 0. Blood samples (approximately 5 and 20 mL) will be collected at Visit Month 0, Visit Month 1, and from Visit Year 1 to Visit Year 6 on a yearly basis to assess HI and CMI responses.

**Revaccination Group:** Subjects (N = 60) to be administered HZ/su vaccine on a 2-dose schedule at Visit Month 0 and Visit Month 2. Blood samples (approximately 5 and 20 mL) will be collected at Visit Month 0, Visit Month 1, Visit Month 3 and from Visit Year 1 to Visit Year 6 on a yearly basis to assess HI and CMI responses.

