**LTFU Group (CMI subset):** Subjects ( $N \leq 234$ ) who were in the CMI subset during study ZOSTER-006 and continue participation in this study. Blood samples (approximately 20 mL) will be collected and tested from Visit Month 0 to Visit Year 6 on a yearly basis to assess CMI responses.

**HZ subset:** Subjects ( $N$  to be determined) who developed confirmed HZ during ZOSTER-006 or ZOSTER-022, or who develop HZ during the interval between the end of the ZOSTER-006/022 and the beginning of ZOSTER-049, or who develop suspected HZ during ZOSTER-049 will be part of the HZ subset. Blood sampling for subjects in the HZ subset is described below.

Subjects who develop HZ at any time after enrolment in ZOSTER-006 or ZOSTER-022 and who are already part of the HI subset in ZOSTER-006 or ZOSTER-022 will provide blood samples to assess HI responses (approximately 5 mL) from Visit Month 0 to Visit Year 6 irrespective of when the HZ episode occurs. If these subjects are part of the ZOSTER-006 CMI subset, then they will also continue to provide blood to assess CMI responses (approximately 20 mL).

Subjects who develop HZ at any time after enrolment in ZOSTER-006 or ZOSTER-022 and who were NOT part of the HI or CMI subsets in these studies, will provide blood samples to assess HI responses (approximately 5 mL) beginning at the annual visit in the ZOSTER-049 study subsequent to the occurrence of the HZ episode. The blood sample taken upon enrolment at Visit Month 0 will be tested and included in the analyses for these subjects.

**1-Additional Dose Group:** Subjects (N = 60) to be administered HZ/su vaccine on a 1-dose schedule at Visit Month 0. Blood samples (approximately 5 and 20 mL) will be collected at Visit Month 0, Visit Month 1, and from Visit Year 1 to Visit Year 6 on a yearly basis to assess HI and CMI responses.

**Revaccination Group:** Subjects (N = 60) to be administered HZ/su vaccine on a 2-dose schedule at Visit Month 0 and Visit Month 2. Blood samples (approximately 5 and 20 mL) will be collected at Visit Month 0, Visit Month 1, Visit Month 3 and from Visit Year 1 to Visit Year 6 on a yearly basis to assess HI and CMI responses.

**Control Group:** Subjects (N = 120) in the non-vaccinated control group. Blood samples (approximately 5 and 20 mL) will be collected at Visit Month 0, Visit Month 1, Visit Month 3 and from Visit Year 1 to Visit Year 6 on a yearly basis to assess HI and CMI responses.

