- To assess persistence of vaccine induced cell-mediated immune responses at Year 5, 6, 7, 8, 9 and 10 and beyond after the primary vaccination in the ZOSTER-006/022 studies **in the CMI subset** in subjects  $\geq 50$  YOA overall and within each of the specified age ranges\* at the time of first vaccination, in the ZOSTER-006 study;
- To assess humoral immune responses at Year 5, 6, 7, 8, 9 and 10 and beyond after the primary vaccination in the ZOSTER-006/022 studies in subjects  $\geq 50$  YOA at the time of first vaccination, in the ZOSTER-006/022 studies, who had a confirmed HZ episode previously for the timepoint considered;
- To assess vaccine induced cell-mediated immune responses at Year 5, 6, 7, 8, 9 and 10 and beyond after the primary vaccination in the ZOSTER-006/022 studies **in the CMI subset** in subjects  $\geq 50$  YOA at the time of first vaccination, in the ZOSTER-006 study, who had a confirmed HZ episode previously for the timepoint considered;
- To assess humoral immune responses one month after the first additional HZ/su vaccine dose (1-Additional Dose and Revaccination groups) and at the same timepoint in the Control group;
- To assess vaccine induced cell-mediated immune responses one month after the first additional HZ/su vaccine dose (1-Additional Dose and Revaccination groups) and at the same timepoint in the Control group;
- To assess humoral immune responses one month after the second additional HZ/su vaccine doses (Revaccination group and at the same timepoint in the Control group);
- To assess vaccine induced cell-mediated immune responses one month after the second additional HZ/su vaccine doses (Revaccination group and at the same timepoint in the Control group);
- To assess persistence of humoral immune responses at Year 1, 2, 3, 4, 5 and 6 timepoints of this study in subjects from the 1-Additional Dose, Revaccination and Control groups;

- To assess persistence of vaccine induced cell-mediated immune responses at Year 1, 2, 3, 4, 5 and 6 timepoints of this study in subjects from the 1-Additional Dose, Revaccination and Control groups;
- To assess vaccine safety and reactogenicity in the 1-Additional Dose and Revaccination groups;
- To assess vaccine safety in the LTFU and Control groups.

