## 5.7. Elimination from study cohorts

*The elimination code and elimination type applicable for cohorts are mentioned below:*

Cohort	Elimination codes	Eli Type
TVC – Randomized groups	900, 1030	M3
TVC for humoral persistence – LTFU	900, 2130, 3615, 3616, 2110	F0 - F6 T1 - T9
TVC for CMI persistence – LTFU	900, 2130, 3615, 4130, 2111	F0 - F6 T1 - T9
TVC for immunogenicity persistence – Randomized groups	900, 1030	L1 - L6
HZ subset for HI	900, 901, 2110 for HI	HS1-HS6
HZ subset for CMI	900, 901, 2111 for CMI	HS1-HS6
TVC Efficacy – LTFU and Control group	900, 901	EF
mTVC – LTFU and Control group	900, 901, 1071, 1501, 2501, 3501	E2, E4, EF
ATP cohort for efficacy - LTFU and Control group	900, 901, 1040, 1041, 1051, 1061, 1071, 1081, 1091, 1501, 1600, 1601, 2040, 2041, 2050, 2051, 2070, 2071, 2081, 2501, 3501	EF
ATP cohort for immunogenicity - Randomized groups*	900, 1030, 1040, 1050, 1070, 1080, 1090, 1600, 2040, 2050, 2060, 2070, 2080, 2090, 2100, 2500	M3
ATP cohort for immunogenicity persistence - Randomized groups*	900, 1030, 1040, 1050, 1070, 1080, 1090, 1600, 2040, 2050, 2060, 2070, 2080, 2100, 2500	L1 – L6
ATP cohort for humoral persistence – LTFU	900, 901, 1040, 1041, 1051, 1061, 1071, 1081, 1091, 1501, 1600, 1601, 2040, 2041, 2050, 2051, 2060, 2061, 2070, 2071, 2081, 2100, 2130, 2501, 3615, 3616, 2110	F0 - F6 T1 - T9
ATP cohort for CMI persistence – LTFU	900, 901, 1040, 1041, 1051, 1061, 1071, 1081, 1091, 1501, 1600, 1601, 2040, 2041, 2050, 2051, 2060, 2061, 2070, 2071, 2081, 2100, 2130, 2501, 3615, 3616, 4130, 2111	F0 - F6 T1 - T9

\*In OPS, to reduce the number of tables, “Adapted ATP cohort for immunogenicity - Randomized groups” is used in tables that include both immunogenicity and persistence of immunogenicity results, i.e., Month 0, 1, 3 and each year follow-up in ZOSTER-049.

*The specification of each elimination code is presented in the Sections [11, 12, 13, 14, 15, and 16](#) of the SAP.*

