HS0	Persistence analysis at M0 – HZ subset
HS1	Persistence year 1 (Month 12) after start of Zoster 049 (Month 0) – HZ subset
HS2	Persistence year 2 (Month 24) after start of Zoster 049 (Month 0) HZ subset
HS3	Persistence year 3 (Month 36) after start of Zoster 049 (Month 0) HZ subset
HS4	Persistence year 4 (Month 48) after start of Zoster 049 (Month 0) HZ subset
HS5	Persistence year 5 (Month 60) after start of Zoster 049 (Month 0) HZ subset
HS6	Persistence year 6 (Month 72) after start of Zoster 049 (Month 0) HZ subset

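### As written, the confirmed-HZ immune analysis does not exclude samples drawn before the episode, and its elimination types follow ZOSTER-049 visits, so it does not match its Year 5-10 post-HZ objective

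*SAP*

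**What the plan says.** The objective (SAP 3.2; Protocol 2.2) sets two conditions. The time scale is years since primary vaccination: "To assess humoral immune responses at Year 5, 6, 7, 8, 9 and 10 and beyond after the primary vaccination". The population is subjects "who had a confirmed HZ episode previously for the timepoint considered". A parallel objective covers the CMI subset.

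The analysis rule (SAP 6.3.2; Protocol 11.7.3.2 is similar) is to tabulate "at each time point when a blood sample result is available on subjects who had a confirmed HZ case". It gives seropositivity and GMC for HI, and descriptive statistics of CD4+ T-cell frequency for CMI.

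Sampling in the HZ subset (SAP 2; Protocol 3) depends on earlier subset membership:

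- HI-subset members with HZ give blood "from Visit Month 0 to Visit Year 6 irrespective of when the HZ episode occurs"; those also in the CMI subset continue CMI sampling.
- Subjects outside the HI and CMI subsets give HI samples "beginning at the annual visit in the ZOSTER-049 study subsequent to the occurrence of the HZ episode". Of their enrolment sample the plan adds: "The blood sample taken upon enrolment at Visit Month 0 will be tested and included in the analyses for these subjects".

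The elimination codes for the HZ subset (SAP 5.7) are "900, 901, 2110 for HI", with 2111 in place of 2110 for CMI. The types assigned there are HS1 to HS6. Appendix 1 of the SAP describes HS1 as "Persistence year 1 (Month 12) after start of Zoster 049 (Month 0) – HZ subset". It also defines HS0 for Month 0, which SAP 5.7 does not assign. The years-since-dose-2 types, T1 to T9, go only to the LTFU persistence cohorts.

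**The concern.** Neither condition of the objective is carried into the analysis section, and other parts of the plan bring pre-episode samples in. The protocol treats HZ as an intercurrent condition able to confound the immune response (Glossary; Section 7.7), so samples from before and after HZ should not share one GMC when the question is the response after HZ. If HZ raises anti-gE, mixing them pulls the early estimates down. Because the pre-HZ share falls at each later visit, it could also create an apparent rise over time.

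The time axis is a second gap. A table by ZOSTER-049 visit does not report Years 5 to 10 after vaccination. The ATP tables that are on that axis cannot stand in, because SAP 5.5 drops subjects from that cohort once HZ has occurred.

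**Working it through.** The plan gives no figure to reproduce. The check compares the rules and then sizes the effect under stated assumptions.

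**Which samples can pre-date HZ**

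- HZ confirmed in ZOSTER-006/022: every ZOSTER-049 sample is after HZ.
- HZ during ZOSTER-049, subject outside the HI/CMI subsets: annual samples start after the episode. Only the Month 0 sample pre-dates it.
- HZ during ZOSTER-049, HI- or CMI-subset member: all samples up to the episode pre-date it. With HZ between the Year 4 and Year 5 visits, that is four annual samples (Years 1 to 4), or five with Month 0.
- SAP 5.7: none of codes 900, 901, 2110 and 2111 depends on the date of HZ. By contrast, the LTFU persistence cohort has a time-dependent HZ rule (SAP 5.5; code 2060 in Appendix 4). The HZ subset lacks the mirror of it.

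**Time axis**

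SAP 6.3.3 assigns the first ZOSTER-049 visit to timeframe 4, 5 or 6 after dose 2 and adds one per yearly visit:

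| ZOSTER-049 visit | Years after dose 2 |
|---|---|
| Month 0 | 4, 5, 6 |
| Year 1 | 5, 6, 7 |
| Year 2 | 6, 7, 8 |
| Year 3 | 7, 8, 9 |
| Year 4 | 8, 9, 10 |
| Year 5 | 9, 10, 11 |
| Year 6 | 10, 11, 12 |

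Each visit mixes three post-vaccination years. The nine years 4 to 12 are exactly T1 to T9.

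**Size in the humoral table (illustration)**

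Assumptions: only cases arising in ZOSTER-049; onset equally likely in study years 1 to 6; full attendance; HI-subset share of cases s = 1,729/14,448 = 0.1197, from the maximum numbers in SAP 2.

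At the Year v visit:

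- pre-HZ samples, from HI-subset cases not yet affected: s(6 − v)/6
- all samples: s + (1 − s)v/6
- pre-HZ share f = the first divided by the second

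If HZ multiplies anti-gE by k (assumption), the reported GMC is k^(−f) of the post-HZ GMC.

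| Visit | Pre-HZ | All | f | k = 2 | k = 4 |
|---|---|---|---|---|---|
| Year 1 | 0.0998 | 0.2664 | 37% | 0.77 | 0.60 |
| Year 2 | 0.0798 | 0.4131 | 19% | 0.87 | 0.77 |
| Year 3 | 0.0599 | 0.5599 | 11% | 0.93 | 0.86 |
| Year 4 | 0.0399 | 0.7066 | 6% | 0.96 | 0.92 |
| Year 5 | 0.0200 | 0.8533 | 2% | 0.98 | 0.97 |
| Year 6 | 0 | 1.0000 | 0% | 1.00 | 1.00 |

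Over the six annual visits: 0.299/3.799 = 8%. With k = 2 and no true change after HZ, the table would show a rise of 1/0.77 = 1.3-fold from Year 1 to Year 6.

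In any Month 0 column, 100% of samples from these cases pre-date HZ.

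The CMI table lacks this dilution, because HZ-subset members outside the HI/CMI subsets give only HI blood. For CMI-subset cases arising in ZOSTER-049, the same assumptions give (6 − v)/6: 83%, 67%, 50%, 33%, 17% and 0%. That subset has at most 234 members, and SAP 6.3.2 reports no geometric mean for it, so no ratio is attached.

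**The case against.** The best reply is that SAP 6.3.2 should be read together with the objective, which already requires HZ before the timepoint. The section does not say that pre-HZ samples are used. HS and T are elimination types, not table layouts: the SAP leaves table format to the separate output specification, and years since dose 2 are already derived for the LTFU group. SAP 5.7 omits HS0, so Month 0 may not be tabulated at all. The result is one descriptive secondary table with no success criterion (Protocol 2; SAP 3), and no accepted immune correlate of protection exists (Protocol 6.7.5).

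Much of this stands. A reader might infer that the analysis certainly uses every available sample. The documents do not show that; they show that nothing excludes pre-HZ samples. A reader might also infer that the objective goes unanswered. That is too strong, because all ZOSTER-049 samples from ZOSTER-006/022 cases and all annual samples from non-subset subjects are after HZ, and the dates needed for the right table are collected.

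The reply does not remove the mismatch. The plan states outright that the Month 0 sample enters the analyses and that HI-subset sampling ignores the HZ date. SAP 2 and Appendix 1 provide for a Month 0 analysis that SAP 5.7 leaves out. Two programmers could produce different tables from this text.

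**Conclusion.** The point holds in a limited form. Followed as written, SAP 6.3.2 with SAP 2 and 5.7 does not exclude pre-HZ samples, and the HZ-subset types follow ZOSTER-049 visits. The analysis therefore does not match its own objective.

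The effect is concentrated at early visits and is gone by Year 6. The shares rest on the assumed HI share, uniform onset and full attendance. The GMC ratios also rest on an assumed effect of HZ on anti-gE. Adding ZOSTER-006/022 cases would lower the shares, since all their samples here are post-HZ.

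A reader might expect half or three quarters of the humoral samples to pre-date HZ, which would give ratios of 0.71 or 0.59 for a two-fold effect. The design does not support that at annual visits under these assumptions; the largest share is about 37%. Higher shares arise only in a Month 0 column, or in the small CMI table.

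The plan should be corrected, but the analysis is secondary and descriptive. VE and the ATP persistence analyses, which exclude HZ, are unaffected.

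**What to change.** - In SAP 6.3.2, count a sample only if it was drawn after onset of the subject's first confirmed HZ.
- Show pre-HZ samples, including the Month 0 sample of later cases, separately if they are shown at all.
- Tabulate by the years-since-dose-2 timeframes of SAP 6.3.3.
- Reconcile HS0 between SAP 5.7 and Appendix 1.
- Align the sentence that puts the Month 0 sample into the analyses, in SAP 2 and in the protocol (Synopsis, Section 3, Table 4 and Section 6.5.8.1). Changing the SAP alone would leave the two documents in conflict.

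The cost is wording in both documents and table programming on dates already collected; no new data are needed. The downside is fewer samples per cell at early timepoints.

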### 6.3.3. Analysis of persistence (immune subset of LTFU group)

Since the interval between the end of ZOSTER-006/022 studies and the start of this study will vary per subject and is dependent on receipt of approval or implementing the study in the different participating countries, some results from the first blood sample may correspond to year 5, year 6 or year 7 post vaccination. To be able to complement the modelling prediction by descriptive data analysis, yearly timeframes will be defined around the anniversary date post vaccination. The details of the set up for these intervals is described below.

*The timeframe of first visit of ZOSTER-049 study in LTFU group will be computed between the date of the first visit of ZOSTER-049 study and the second dose administration date of previous ZOSTER-006/022 studies.*

*Time frame of first visit = (date of the first visit of ZOSTER-049 - date of vaccination dose 2 in ZOSTER-006/022+1) /365.25.*

*The result of the first visit will be assigned to each yearly timeframe derived as follow*

Timeframe of first visit	Allowed interval for computed time of first visit	Lower bound of timeframe of first visit	Upper bound of timeframe of first visit
4	[3.5, 4.5)	[3.5	4.5[
5	[4.5, 5.5)	[4.5	5.5[
6	[5.5, 6.5)	[5.5	6.5[

***Yearly timeframe for the persistent analysis in LTFU will be calculated by adding 1 year to the timeframe of first visit for each subsequent visit.***

